9.3.1 Sensitivity Analysis of the Primary and Secondary Endpoints

The primary and secondary endpoint analyses will be repeated for the RF and MMIA analysis sets as noted those respective sections.

Additionally, the analysis of ORS at Weeks 12, 24, 36, and 52, and the number and percentage of subjects with 12- and 24-week confirmed improvement for the EDSS+ and each of its components will be repeated based on multiple imputation (MI). First, a full dataset will be imputed using full data imputation MCMC. Data will be imputed for the

EDSS, T25FW, 9HPT-D and 9HPT-ND in a continuous fashion for each endpoint separately. Then, the definition of clinically significant improvement/no change/clinically significant worsening as seen in Section 4.3.1 will be applied to determine the components of the ORS or 12- or 24- week confirmed improvement status. The imputation model will include treatment group, type of MS, baseline use of immunomodulator therapies, baseline variable for the respective endpoint being imputed, and the non-missing post-baseline values for the variable that will be imputed (value at Week 12, 24, 36, 52, 64 and 76). The number of imputed datasets will be 30, and the random seed will be 123455. The ORS at each visit noted above will be summarized for each treatment group and compared to placebo using ANCOVA, with baseline values for each component of the EDSS + included in the model. The responder status with 12- and 24-week confirmed improvement will be analyzed with a logistic regression as noted in Section 9.4.1.

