2.1 Individual Treatment Period Visit Activities

This section presents a list of activities performed during each visit, organized by visit.

Study procedures may be split over 2 consecutive days, with the study drug administration to occur on the second day. At the Week 0 Baseline Visit, the site will conduct actigraphy training with the subject, and application of sensors should be done on the same day as the timed 25-foot walk. These activities (along with all the pre-dose activities) should occur before dosing.

Activities are grouped by category (Interview, Exam, etc.). Further information about each activity is provided in Section 3.

COVID-19 Pandemic-Related Acceptable Protocol Modifications

During the COVID-19 pandemic, if it is not possible for all study procedures to be performed as specified due to travel restrictions or other reasons, the following modifications are allowed:

- Some study visits and/or activities may be performed by phone/virtually. These are indicated by a hashtag (#) in the appropriate visit table(s) below.
 - During a virtual visit, activities that do not need to be performed are indicated by a minus sign (-).
- Some study visits and/or activities may be performed by a local laboratory. These are indicated by a plus sign (+) in the appropriate visit table(s) below. All procedures performed at local facilities must be performed by appropriately qualified personnel.
- Study Visits and/or activities should be performed as scheduled whenever possible. If it is not possible to do so due to the pandemic, the following modifications are allowed:
 - Study procedures may be split over 7 consecutive days. The Expanded Disability Status Scale (EDSS), 9-Hole Peg Test (9HPT), or Timed 25 Foot Walk (T25FW) should all occur on the same visit day.
 - MRI assessments may be collected up to 12 weeks after the projected visit for the missed timepoints at Week 24 and 52 with the sponsor's consent due to reasons related to the COVID-19 pandemic. However, all MRI assessments projected to be obtained on or before mid-November 2020 must be completed by the end of November 2020. To accommodate scheduling of the vast volume of projected Week 52 MRIs in December 2020, at the discretion of the sponsor, sites may schedule Week 52 MRIs up to -28 days of their projected Week 52 visit.

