- Multiple Sclerosis Individualized Outcome Assessment (MSIOA): The MSIOA is a novel clinicianreported outcome assessment that has been developed for this study to identify the impact of MS and MS treatment on an individual subject's activities of daily living across multiple domains. MS affects subjects differently and the importance of certain abilities is different for each subject. This outcome will determine the areas of daily living (based on existing activities of daily living [ADLs] within the MSIS) that are most impacted and most important to each subject and these will be ranked on a standardized, ordinal rating scale and tracked during the course of the study.
- Expanded Disability Status Scale Plus (EDSS+) is comprised of the following three scales:
 - EDSS: The Expanded Disability Status Scale (EDSS) is a method of quantifying disability in multiple sclerosis and monitoring changes in the level of disability over time. The EDSS scale ranges from 0 to 10, with 0 referring to normal neurological examination and 10 referring to death. It changes in 0.5 unit increments that represent higher levels of disability. Scoring is based on an examination by a neurologist. It takes about 15 30 minutes to conduct the neurological examination and do the scoring.
 - Timed 25-Foot Walk (T25FW): The T25FW quantifies the MS subject's mobility and leg function during a timed walk over a designated and clearly marked twenty-five foot course. The subject is to walk as quickly and safely as possible over the course to the designated twenty-five foot mark. The walk is measured in seconds from the time the initial instructions are provided to the subject reaching the twenty-five foot mark. The subject is then instructed to walk quickly and safely following the course back to the starting point. Again the time for the walk is recorded in seconds. The T25FW will be conducted by a trained examiner. The examiner does not necessarily have to be a nurse or physician. Assistive devices (i.e., cane, crutches, walker) may be used. Scoring is the average of the two trial walks. Additional instructions will be provided for scoring of individuals unable to complete the walk due to severity of impairment. Total time to administer the T25FW is 1 5 minutes.

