4.3 Endpoint

4.3.1 Primary Efficacy Endpoint

The primary efficacy endpoint is the Overall Response Score (ORS) at Week 52.

ORS is a composite score derived from 4 components:

- Expanded Disability Status Scale (EDSS)
- Timed 25-Foot Walk (T25FW)
- 9-Hole Peg Test in the dominant hand (9HPT-D)
- 9HPT in the non-dominant hand (9HPT-ND)

The EDSS + is a composite derived from the EDSS, T25FW, 9HPT-D and 9HPT-ND where responder status is defined as a clinical meaningful improvement on one or more of these endpoints. Hereafter, the EDSS, T25FW, 9HPT-D and 9HPT-ND will also be referred to as "components of the EDSS +" or "components of the ORS."

The ORS is scored with a range from -4 to +4 at each assessment for all post-baseline visits. Scores for each component are assessed relative to their baseline value: -1 if there is clinically significant worsening, 0 if the change does not meet the clinically significant threshold criteria, or +1 if there is clinically significant improvement. The scores for all components are summed at each assessment. If any of the 4 components of the ORS are missing within a visit window, then the ORS will be considered missing for that visit.

The clinically significant change thresholds for EDSS, T25FW and 9HPT are provided in the following table.

ORS Components	Score of ORS Components at Post-Baseline Visits		
	-1 (Clinically Significant Worsening)	0 (No Clinically Significant Change)	1 (Clinically Significant Improvement)
EDSS change from baseline	≥ 1 if baseline EDSS ≤ 5.5 ; ≥ 0.5 if baseline EDSS ≥ 6.0	-0.5, 0 or 0.5 if baseline EDSS ≤ 5.5 ; 0 if baseline EDSS ≥ 6.0	≤ -1 if baseline EDSS ≤ 5.5 ; ≤ -0.5 if baseline EDSS ≥ 6.0
T25FW change from baseline	$\geq 20\%$	$> -20\%$ and $< 20\%$	$\leq -20\%$
9HPT-D change from baseline	$\geq 20\%$	$> -20\%$ and $< 20\%$	$\leq -20\%$
9HPT-ND change from baseline	$\geq 20\%$	$> -20\%$ and $< 20\%$	$\leq -20\%$

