4.4 Sample Size Justification

Approximately 165 subjects will be equally randomized 1:1:1 to each treatment group (approximately 55 subjects in each treatment, with at least 20 rSPMS subjects and approximately 35 RRMS subjects). There is limited prior data to estimate the magnitude of effect and variance. This sample size will have approximately 80% power to detect an

effect size (ES) of 0.43 with significance level of 0.1 and overall dropout rate of approximately 10%, using a 1-sided t-test.

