4.7 Missing Data Imputation

For continuous efficacy variables, data will be summarized using a mixed-effect model for repeated measures (MMRM) model unless otherwise specified. Missing data will not be imputed before applying an MMRM model. The MMRM model relies on a missing at random (MAR) assumption.

For sensitivity analyses of the primary and secondary efficacy variables, missing values will be imputed using multiple imputation (MI) and categorized as responder/non-responder after imputation. The MI model also relies on a MAR assumption.

Justification for the MAR Assumption:

The COVID-19 pandemic is interfering with the conduct of many ongoing trials, with potential impact on treatment duration and the collection, analysis and the interpretation of clinical trial data. Some protocol-specified visits in this clinical trial may be impacted due to COVID-19 infection or logistical restrictions during the pandemic. For example, some scheduled visits may be missed due to self-quarantine or local government restrictions on travel; some visits may also be delayed or canceled due to healthcare resource constraints during the pandemic. These missed visits will be recorded in the

database. The probability of having missed visits and missing data due to COVID-19 infection or logistical restrictions related to the COVID-19 pandemic can be reasonably assumed to be unrelated to the unobserved values conditional on the observed data.

Therefore, for the purpose of statistical analysis, it is reasonable to assume that these missing data are missing at random (MAR) and the statistical models that require MAR assumption are appropriate. In some cases, sensitivity analyses may be performed to assess the impact of missing data and the robustness of the conclusion.

Where noted, summaries as observed will not impute values for missing evaluations, and thus a subject who does not have an evaluation on a scheduled visit will be excluded from the as observed for that visit.

Safety variables will be summarized as observed.

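### SAP 9.3.1 imputes EDSS as a continuous value and states no return to the 0.5-point scale before the cut-offs are applied, so imputed EDSS events are likely to be under-counted

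*SAP*

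**What the plan says.** SAP 9.3.1 creates a full dataset by MCMC multiple imputation (30 datasets), drawing "EDSS, T25FW, 9HPT-D and 9HPT-ND in a continuous fashion for each endpoint separately". Besides treatment group, type of MS, baseline immunomodulator use and the component's own baseline, the predictors are "the non-missing post-baseline values for the variable that will be imputed". The 4.3.1 definitions of improvement, no change and worsening are applied afterwards. SAP 4.7 gives the same order: missing values are imputed and then "categorized as responder/non-responder after imputation". Neither section mentions rounding, an ordinal model or predictive mean matching.

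SAP 4.3.1 sets the EDSS cut-off at 1 point for baseline up to 5.5 and 0.5 point for baseline 6.0 or more. The table's no-change cell lists only half-step values; for the lower band it reads, after a leading minus sign, "0.5, 0 or 0.5 if baseline EDSS" up to 5.5. The text above the table gives a general rule: "0 if the change does not meet the clinically significant threshold criteria". The Operations Manual, Section 3.6, says of EDSS: "It changes in 0.5 unit increments that represent higher levels of disability".

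The imputed data feed four places: the repeat of the ORS analysis and of 12- and 24-week confirmed improvement (9.3.1), the repeat of the EDSS and EDSS+ response regression (9.3), and disability progression (9.4.2). In 9.3, improvement also has a non-responder and an as-observed version. In 9.4.2, progression is based on the imputed dataset alone.

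**The concern.** The cut-offs were written for a score that moves in half steps. For an observed subject, a change of one full point is simply the first grid value that counts as an event. For a continuous draw the same cut-off is stricter, because every draw lying between the grid midpoint and the cut-off is scored 0. Imputed subjects are then judged by a harder EDSS rule than observed subjects, and the sensitivity analysis mixes a scoring artefact with the missing-data question that it is meant to answer.

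What is at stake is the accuracy of reported EDSS improvement and worsening rates in the imputed analyses. It matters most for EDSS and EDSS+ progression, because no unimputed analysis is planned beside it. The SAP's own summary of changes cites increased missing data from the pandemic, so the imputed share may not be trivial.

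**Working it through.** **Inputs from the documents.** Half-point EDSS steps (Operations Manual 3.6); cut-offs of 1.0 and 0.5 (SAP 4.3.1); about 55 subjects per arm and "overall dropout rate of approximately 10"% (SAP 4.4). The SAP's design figure reproduces: 55 x 0.9 = 49.5 per arm, and Phi(0.43 x sqrt(49.5/2) - 1.2816) = 0.80, the stated power. The present point does not depend on it.

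**Inputs assumed.** The documents give no SD or shape for EDSS change, so ranges are used.

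**Step 1, one draw.** Let the underlying change be N(0, SD), recorded to the nearest 0.5. A recorded improvement then means an underlying change of -0.75 or lower (baseline up to 5.5), or -0.25 or lower (baseline 6.0 or more). The imputation model sees the recorded values, so its draws have variance SD^2 + 0.25/12 and are cut at -1.0 or -0.5. For SD 0.5 the draw SD is sqrt(0.25 + 0.0208) = 0.520. The true rate is Phi(-0.75/0.5) = 6.7%, and the drawn rate is Phi(-1.0/0.520) = 2.7%.

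| SD | baseline up to 5.5: true / drawn | baseline 6.0 or more: true / drawn |
|---|---|---|
| 0.4 | 3.0% / 0.9% | 26.6% / 12.0% |
| 0.5 | 6.7% / 2.7% | 30.9% / 16.8% |
| 0.7 | 14.2% / 8.1% | 36.0% / 24.2% |
| 0.9 | 20.2% / 13.6% | 39.1% / 29.2% |

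With mean change 0, worsening is the mirror image.

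**Step 2, simulated trials.** 3 x 55 subjects, 15% missing at Week 52, an active shift of 0.3 SD, 250 trials per setting. Rates in imputed subjects; the ranges cover different predictor sets, with and without Weeks 64 and 76:

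| SD | improvement: true / SAP | worsening: true / SAP |
|---|---|---|
| 0.4 | 7.7% / 3.7-4.0% | 3.7% / 1.7% |
| 0.5 | 12.4% / 6.9-7.3% | 6.5% / 3.3-3.4% |
| 0.6 | 17.7% / 10.7-11.2% | 9.0% / 5.5% |
| 0.7 | 22.0% / 14.5-15.0% | 11.7% / 7.6-7.8% |
| 0.8 | 25.6% / 18.0-18.5% | 14.5% / 9.7-10.0% |

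The loss runs from (25.6 - 18.5)/25.6 = 28% to (7.7 - 3.7)/7.7 = 52% of improvements, and from 31% to 54% of worsenings.

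**Step 3, other shapes.** A separate simulation made half the subjects stable and took SD 0.6, 0.8 and 1.0 in the rest. It gave true / SAP improvement of 8.8 / 4.7%, 11.8 / 8.2% and 14.5 / 11.2%. The under-count remains but shrinks as the SD grows: 47%, 31% and 23% of events.

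The direction can also reverse. Take baseline 6.0 or more with 84% unchanged and 3%, 3% and 2% moving 0.5, 1.0 and 1.5 points each way. True improvement is 8%. The variance is 2 x (0.03 x 0.25 + 0.03 x 1 + 0.02 x 2.25) = 0.165, the SD is 0.406, and a normal draw gives Phi(-0.5/0.406) = 10.9%. A more extreme case gave 12% true against 22.7% drawn.

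**Step 4, whole arm.** Multiply the deficit in imputed subjects by the missing share. Worsening at SD 0.5: (6.5 - 3.4) x 0.10 = 0.3 points. Improvement at SD 0.7: (22.0 - 14.5) x 0.20 = 1.5 points. Direct simulation for SD 0.5-0.7 gave improvement 0.6-0.7 points low at 10% missing and 1.2-1.7 at 20%, and worsening 0.3-0.9 low.

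**Step 5, comparisons.** In the composite simulations the ORS arm difference moved by at most 0.012 and the EDSS+ log odds ratio by at most 0.045. For scale, the standard error of a 27% rate in 55 subjects is sqrt(0.27 x 0.73/55) = 6.0 points.

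**The case against.** Four objections carry weight.

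First, the SAP does not say that draws stay unrounded. It refers to a separate statistical programming plan, which could contain a grid step. This stands as a limit: the supportable claim is that the SAP states no such step.

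Second, a reader might infer that imputed EDSS rates are always too low. The documents give no distribution for EDSS change, and the counter-examples in Step 3 show that the direction can reverse at baseline 6.0 or more. The claim must stay conditional.

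Third, a reader might go further on the imputation model. One inference is that a -0.7 draw has no category; the general rule in 4.3.1 scores it 0. Another is that, because the components "should all occur on the same visit day" and are imputed separately, a missed visit leaves four unrelated draws. Each draw conditions on that component's own earlier visits, which carry part of the cross-component correlation: with a true correlation of 0.30, separately imputed draws still correlated 0.12-0.22. Nor do the documents show a defect in the scale of the timed tests, since 9.3.1 specifies neither raw nor log seconds. The sign of any error in the EDSS+ composite depends on that choice, so no direction is claimed for the composite.

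Fourth, materiality is low. The primary MMRM does not impute, the non-responder and as-observed results are unaffected, progression is exploratory, and SAP 9.6 already plots component worsening as observed. All of this is correct and sets the severity. It does not close the gap in 9.4.2, because that plot is by component and gives no EDSS+ progression rate.

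**Conclusion.** The point holds as a minor one. As written, 9.3.1 applies half-step cut-offs to continuous EDSS draws, which scores 0 for draws whose nearest EDSS step is an event. If changes are roughly normal, or many subjects are stable with modest changes, imputed EDSS improvement and worsening are under-counted, by about a quarter to a half or more of events in most settings tested. On a whole arm at 10-20% missing, that is about 0.3 to 1.7 points.

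These sizes rest on assumed SDs and shapes, and on the SAP's silence meaning that no grid step is applied. The effect is confined to the multiple-imputation repeats of ORS, confirmed improvement and EDSS/EDSS+ response, and to exploratory EDSS and EDSS+ progression. It gives no ground for doubting the primary result or the treatment comparisons.

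**What to change.** - **SAP 9.3.1:** impute the EDSS change from baseline by predictive mean matching, for example with 5 donors, so that only half-step values occur. In the Step 2 settings this gave improvement of 7.9-8.0% at SD 0.4 (true 7.7%) and 25.5-26.0% at SD 0.8 (true 25.6%). Match on the change, not the raw score: at baseline 6.0 or more, raw-score matching gave 37.6-50.8% against 34.1-45.8% true, and matching on the change gave 34.5-47.1%.
- **Do not rely on rounding alone.** It tends to over-count when many subjects are stable: in the Step 3 simulation with half the subjects stable it gave 10.8, 15.2 and 18.3% against 8.8, 11.8 and 14.5% true.
- **SAP 9.4.2:** present EDSS+ and component progression as observed beside the imputed result.
- **Status:** Protocol Appendix E reports that the planned efficacy analysis has been done, so label any rerun post hoc. If there is no rerun, add a footnote that continuous EDSS draws may under-count imputed EDSS events.

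The cost is slightly more programming and one more table; no new data are needed.

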4.2.2 Variables used for Stratification at Randomization

Randomization will be stratified by diagnosis of MS form [relapsing remitting MS (RRMS) vs. relapsing secondary-progressive MS (rSPMS)], and presence of background MS immunotherapy (Yes vs. No).

The stratification variables used in the analyses will be based on the MS type from the MS Disease History eCRF and MS immunotherapy on the first dose date from the Concomitant Medications eCRF.

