9.2 Primary Efficacy Analysis

The primary efficacy variable is the ORS at Week 52 and secondary efficacy variables are the ORS at Weeks 12, 24, and 36. The ORS will be summarized continuously as observed (including n, mean, standard deviation, minimum, median and maximum) at each visit.

The frequency and percentage of subjects with each ORS score in the range of -4 to +4 will also be provided by treatment group at each visit. The data will be summarized as observed, i.e., no imputations will be implemented.

The comparisons between the each elezanumab group and placebo for the primary efficacy endpoint ORS at each scheduled visit during the treatment period will be performed using anMMRM. The ORS for each treatment group at scheduled visits and overall will be estimated from the model. The within group LS mean 95% confidence interval, pooled standard deviation, effect size, and 95% confidence interval for the effect size will also be presented by treatment group. The model will include the fixed effects of treatment, visit, the stratification factors of diagnosis of MS (RRMS or rSPMS) and background MS immunotherapy (Yes or No), and the treatment-by-visit interaction, with baseline scores (EDSS, T25FW, 9HPT-D, 9HPT-ND) as covariates. The REPEATED statement will be used for visit with blocks in the covariance matrix identified by subject nested within treatment group. The unstructured covariance structure will be used to estimate the within subject variance-covariance. If the model fails to converge, the first order autoregressive (AR[1]) covariance structure will be substituted. If the model still fails to converge, the compound symmetry (CS) covariance structure will be substituted. Denominator degrees of freedom will be computed using the Kenward-Roger method.

This will be repeated for the RF and MMIA sets.

The posterior probability that each elezanumab group's effect size is greater than 0.1, 0.3, and 0.5 will be presented for the mITT analysis set.

The ORS and corresponding 95% confidence interval based on the MMRM for the mITT analysis set will be plotted at each time point during the treatment period by treatment group.

The post-treatment ORS scores will be summarized continuously as observed.

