The model for the change from baseline analysis will include treatment, the stratification factors of diagnosis of MS (RRMS or rSPMS) and background MS immunotherapy (Yes or No), and the baseline value. For each treatment group, the number of subjects, mean, standard deviation, minimum, and maximum, will be presented, as well as the LS means and standard error, and the between group difference, standard error, and 95% confidence interval.

The change from baseline in lesion MTR for T1 GAD-enhancing lesions and delta MTR will be analyzed using an MMRM. The change from baseline will be calculated for each unique lesion within a treatment group. A dummy code will be created based on each subject-lesion to describe each unique lesion. The model will include the fixed effects of treatment, visit, the stratification factors of diagnosis of MS (RRMS or rSPMS) and background MS immunotherapy (Yes or No), and the treatment-by-visit interaction, with baseline MTR value as a covariate. The RANDOM statement will be used for each subject. The REPEATED statement will be used for visit with blocks in the covariance matrix identified by unique lesion nested within subject nested within treatment group. The unstructured covariance structure will be used to estimate the within subject variance-covariance. If the model fails to converge, the first order autoregressive (AR[1]) covariance structure will be substituted. If the model still fails to converge, the compound symmetry (CS) covariance structure will be substituted. Denominator degrees of freedom will be computed using the Kenward-Roger method.

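### The ANCOVA on multiply imputed ORS in SAP 9.3.1 names neither randomisation stratum, and no prespecified ORS analysis departs from missing at random

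*SAP*

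**What the plan says.** **Strata.** SAP 4.2.2 states: "Randomization will be stratified by diagnosis of MS form", with background MS immunotherapy as the second factor. The primary MMRM for ORS (SAP 9.2) includes "the stratification factors of diagnosis of MS (RRMS or rSPMS) and background MS immunotherapy (Yes or No". Protocol 7.3 puts stratification factors in the ORS model and in the logistic models for binary endpoints. Within SAP 9.3.1, "The imputation model will include treatment group, type of MS, baseline use of immunomodulator therapies", among other terms. The later comparison of imputed ORS is described only as "compared to placebo using ANCOVA, with baseline values for each component of the EDSS + included in the model". The EDSS+ improvement model in SAP 9.3 lists the four component baselines and treatment, without strata.

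**Missing data.** SAP 4.3.1 sets the rule for the composite: "If any of the 4 components of the ORS are missing within a visit window, then the ORS will be considered missing". SAP 4.7 says the MMRM relies on MAR and adds: "The MI model also relies on a MAR assumption". Its justification is that "missing data due to COVID-19 infection or logistical restrictions related to the COVID-19 pandemic can be reasonably assumed" to be unrelated to the unobserved values, given the observed ones. Further sensitivity analyses are left optional, with no method or trigger. Operations Manual 4.1 describes discontinuation recorded as disease progression, and discontinuation when a relapsing subject starts an immunomodulator that the protocol does not list.

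**The concern.** A sensitivity analysis should differ from the primary analysis in the assumption under test and, as far as possible, in nothing else. This one drops two covariates for no stated reason. After stratified randomisation, leaving prognostic strata out of the model tends to make the standard error slightly too wide.

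The MAR gap concerns what the check can show. If the primary model and its check share one missing-data assumption, their agreement says nothing about dropout that depends on the unseen Week 52 outcome. The secondary EDSS+ endpoint has non-responder imputation. ORS, the primary endpoint, has no counterpart, and one missing component is enough to make an ORS value missing.

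**Working it through.** **1. The plan's own figure.** Inputs from SAP 4.4: 55 per arm, 10% dropout, effect size 0.43, one-sided 0.1.
- Evaluable per arm = 55 × 0.9 = 49.5. In SD units, SE = √(2/49.5) = 0.201.
- Noncentral t with 97 degrees of freedom and noncentrality 0.43/0.201 = 2.14 gives power 80.2%. The stated figure of about 80% reproduces.
- Smallest effect that passes = t(0.9, 97) × SE = 1.290 × 0.201 = 0.259 SD.

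**2. Where the strata appear.**

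| Step | Strata named? |
|---|---|
| Randomisation, SAP 4.2.2 | yes |
| ORS model, Protocol 7.3 | yes |
| Primary MMRM, SAP 9.2 | yes |
| Imputation model, SAP 9.3.1 | yes |
| Confirmed-improvement logistic model, SAP 9.4.1 (also used in 9.3.1) | yes |
| Change-from-baseline ANCOVA for MRI, SAP 9.4.11 | yes |
| ORS ANCOVA after imputation, SAP 9.3.1 | no |
| EDSS+ logistic model, SAP 9.3 | no |

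**3. Size of the strata effect.** Let R² be the share of residual ORS variance that the strata explain. The documents do not give it, so 2 to 10% is assumed. The SE is multiplied by √(1 − R²), and the effect size becomes 0.43/√(1 − R²).

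| R² | SE factor | SE narrower by | Effect size | Power |
|---|---|---|---|---|
| 0 | 1.000 | – | 0.430 | 80.2% |
| 2% | 0.990 | 1.0% | 0.434 | 80.8% |
| 5% | 0.975 | 2.5% | 0.441 | 81.7% |
| 10% | 0.949 | 5.1% | 0.453 | 83.2% |

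**4. Which ORS analyses test MAR.** The MMRM and the multiple imputation assume it. The repeats in the relapse-free (RF) and minimal-missed-infusion (MMIA) sets use the same MMRM on fewer subjects. The as-observed summaries are descriptive. None of these departs from MAR.

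**5. Scale of a departure.** Assume 10% missing and not COVID-related in an active arm (55 × 0.10 = 5.5, about 5 to 6 subjects), and an ORS SD of 1.1 to 1.4 (not in the documents). Let d be the average number of ORS points that these subjects lose relative to their MAR imputations.
- Fall in the contrast = 0.10 × d/SD, so 0.07 to 0.09 SD per point.
- Using SAP 4.4's one-sided 0.1 level as the yardstick, the loss at which a result stops passing is d = (estimate − 0.259) × SD/0.10.
- Estimate 0.43 SD: 0.171 × 1.1/0.10 = 1.9 points, up to 0.171 × 1.4/0.10 = 2.4 points.
- Estimate 0.30 SD: 0.041 × 1.1/0.10 = 0.4 to 0.5 points, up to 0.041 × 1.4/0.10 = 0.6 points.

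A result at the design effect is therefore fairly robust, while a modest one is not. The useful range of shifts starts below an average of half a point.

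**6. Why the shift belongs on components.** Imputation is by component, and ORS is missing when any one component is. Take a subject with three observed scores of +1 and an imputed 0, so ORS 3. The lowest value compatible with the observed data is 3 − 1 = 2. Subtracting 3 from the total would give 0 and overwrite observed results.

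**The case against.** **On the strata.** The ANCOVA sentence does not name treatment as a model term either, so it may not be a full specification. SAP 9.3.1 also says that the ORS analysis is repeated, which could be read as carrying the strata over. That stands as a reason not to call the omission deliberate. It does not settle the model, because the method changes from MMRM to ANCOVA and the only covariates then named are the baselines. One added phrase settles it under either reading.

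**On MAR.** This is a Phase 2a proof-of-concept trial without multiplicity control, and SAP 9.2 states no success rule. Exit after observed worsening is compatible with MAR, and the Early Discontinuation visit collects all the components. Many relapsing subjects may stay in the trial, and the RF set removes adjudicated relapsers. All of this lowers the urgency. It does not supply a test of MAR: the RF set changes the population, and the imputation model lists only scheduled visits. The SAP gives no rule that maps an early-discontinuation value to one of those visits. The statistical programming plan that it cites is not among the documents and may hold one.

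Protocol Appendix E reports no benefit on any endpoint, so a run that penalises the active arms has no positive result to overturn. The point concerns the plan as written, not that result.

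**Conclusion.** The concern holds, at modest size. The strata should be named in the SAP 9.3.1 ANCOVA and in the SAP 9.3 EDSS+ model. For the ANCOVA the expected gain is 1.0 to 5.1% of a standard error, under the assumed R² of 2 to 10%. The MAR point is secondary: a cheap addition that matters mainly if the estimate is well below the design effect. Its figures rest on the assumed ORS SD and on all of the planned 10% dropout being unrelated to COVID-19.

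Four stronger readings are not supported.
- A reader might infer that the imputed analysis is biased without the strata. Both are in the imputation model, so the imputations already condition on them. What may be lost is a little precision.
- A reader might infer that, once the covariates match, any difference between MMRM and imputation is due to missing data. Model form and component-level imputation would still differ.
- A reader might take dropout off the sample size and also dilute the effect by the same dropouts to show a power loss. That counts the same subjects twice.
- A reader might infer that continuously imputed EDSS changes cannot be scored, because the no-change cell in SAP 4.3.1 lists only half-point values. The text above that table scores 0 whenever no threshold is met, and the cells for ±1 are inequalities, so every imputed value has a score.

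**What to change.** 1. **SAP 9.3.1, ORS ANCOVA:** name treatment, diagnosis of MS, background MS immunotherapy and the four component baselines. Cost: one sentence and two model terms.
2. **SAP 9.3, EDSS+ logistic model:** add the same two factors, in line with Protocol 7.3. Cost: two model terms.
3. **SAP 9.3.1, one delta-adjusted run on the same 30 imputations:** in the elezanumab groups, worsen only the imputed Week 52 component values whose missingness is not recorded as COVID-related. Do this before the SAP 4.3.1 scoring and leave observed components unchanged. Use a graded set of shifts, for example fractions of each component's own threshold in SAP 4.3.1. Report the estimate, 95% CI and effect size at each step. If a tipping step is to be reported, name the criterion in advance, since SAP 9.2 gives none. Cost: one sensitivity table.

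No new data should be needed. SAP 8.5 already summarises the primary reason for each affected visit, and Operations Manual 4.2 provides supplemental forms for COVID-related missed visits. The downside is that the shifts are a judgement and, at 10% missing, act on about 5 to 6 subjects per arm.
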